## 6.4 Evaluation during Follow-up Phase

The following evaluations are completed during the follow-up phase:

Procedure	Evaluation	Timing
Patient status report	Survival status	Once monthly until 1 year from first treatment. After the first year record only the date of death or alive at Year 5 (Day 1825).
	Relapse status New anti-leukemic therapies	Once monthly until 1 year from first treatment. After the first year record only the date of relapse and any new leukemic therapies.
Hematology	Hemoglobin White Blood Count Platelets Differential Count	Once monthly until 1 year from first treatment. After the first year record only the date of relapse and any new leukemic therapies.
Bone Marrow Evaluation	Morphology	For patients in CR or CRi perform at any time that there is a suspicion of relapse . Following the first year of follow up, record relapse information, including any bone marrow evaluations. Not required following relapse.
Diagnostic Imaging	Echocardiography, MUGA or cardiac MRI	If last treatment phase LVEF was reduced >10% from baseline and is less than 50% repeat every 3 months until LVEF returns to baseline $\pm$ 5% or until 1 year from first treatment. Persistent reductions in LVEF of >10% with nadir values below 50% documented at 1 year are considered permanent sequelae.
Biochemistry	BUN Creatinine Electrolytes (Sodium, Potassium, Chloride) Bilirubin Alkaline phosphatase AST or ALT Protein Calcium Albumin Glucose	Perform monthly only if abnormality(ies) persists at the end of the Treatment Phase. Perform until abnormality(ies) returns to baseline, until 1 year from first treatment or the initiation of new therapy and/or relapse. (whichever is earliest)
Adverse Events/Toxicity	CTCAE v.4 assessment	Assess AEs that were ongoing at the time of discontinuation. Do NOT record any new AEs. AEs that persist without evidence of recovery for >30 days are considered permanent sequelae and do not require further follow-up.

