#### 4.6 Follow-up Phase

Patients will be followed at monthly intervals or more frequently depending on clinical circumstances until start of the next salvage treatment, death or for 1 year from date of enrollment. Patients alive and in remission after 1 year will be followed annually or more frequently depending on clinical circumstances for up to 5 years from enrollment. For EFS evaluation, events include: documentation of persistent AML after induction, relapse after achievement of CR/CRp/ CRi, or death. Bone marrow assessments will be performed at any time during follow up when recurrent cytopenias raise the suspicion of AML relapse. After documentation of persistent leukemia or relapse, follow-up for OS will continue. At the start of HSCT or non-protocol AML treatment of any sort or 30-days following the last dose, whichever occurs first, AE data collection will stop.

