### **8.2 Overall Survival**

Overall survival is measured from the date of registration to death from any cause. Patients not known to have died will be censored on the date they were last known to be alive. Patients will be followed for up to 5 years.

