## **11.2 Sample Size and Power Justification for Primary Endpoint**

With 24 months for accrual, and a minimum of 36 months of follow-up, using a one-sided alpha-level of 0.05, a sample size of 30 patients has 80% power to detect a difference between the null hypothesis of 10 months median survival versus 16 months median survival in this patient population.

In regards to safety, with a sample size of 30 the maximum width of the one-sided 95% exact confidence interval for estimated 30-day or 60-day mortality rates is less than 19%.

Analysis of the relationship of cognitive function to outcome and overall survival will be hypothesis generating.

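### After year 1 the follow-up sections disagree, and Section 6.4 taken literally records late deaths but no alive dates before Year 5, so overall survival can be censored according to outcome and biased downward, mainly in the tail

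*Combined protocol and SAP*

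**What the plan says.** Three places in the protocol describe survival follow-up after the first year, and they differ.

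- **Section 6.4**, survival status row: monthly for one year, then "After the first year record only the date of death or alive at Year 5 (Day 1825"). Other rows keep recording dates of relapse and of new anti-leukemic therapy.
- **Section 4.6**: "Patients alive and in remission after 1 year will be followed annually" or more often, up to 5 years. For patients with relapse or persistent leukemia it says that OS follow-up goes on, but gives no interval.
- **Appendix 2**: a patient status report is marked in a column for years 2 to 5 headed with the word once. This can mean once a year or once in the whole period.

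On analysis, Section 8.2 says "Patients not known to have died will be censored on the date they were last known to be alive". Section 11.4 repeats that rule as of the time of analysis and specifies a Kaplan-Meier curve and a median with a Brookmeyer-Crowley interval. It names no test against the null median. Section 11.2 bases its power statement on 24 months of accrual and "a minimum of 36 months of follow-up". No analysis date, data cut-off or vital-status update is given.

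**The concern.** Kaplan-Meier estimation assumes that being censored at a given time says nothing about later survival. Under the literal Section 6.4 rule it says a great deal. A patient who dies in month 30 is recorded as a death in month 30. A patient still alive at the analysis has no recorded alive date after month 12 unless Day 1825 has been reached. After month 12 the risk set then contains only patients already known to die before the cut-off.

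The follow-up in Section 11.2 implies a cut at about 24 + 36 = 60 months after first enrolment. Day 1825 is 1825/365 = 5 years, or 60 months. At that cut the very first patient is only just reaching the Year-5 entry and nearly all other survivors have not.

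OS is the primary efficacy endpoint. At stake are late survival estimates that are too low, and lost power in any test that uses total follow-up time.

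**Working it through.** **Inputs (Section 11.2).** "using a one-sided alpha-level of 0.05"; "a sample size of 30 patients has 80% power to detect a difference"; "null hypothesis of 10 months median survival versus 16 months median survival"; "With 24 months for accrual, and a minimum of 36 months of follow-up". Added assumptions: exponential survival, uniform accrual, no loss to follow-up, every death up to the cut-off known. Each patient then has 36 to 60 months of potential follow-up. Monthly hazards are ln 2/10 = 0.0693 (null) and ln 2/16 = 0.0433 (alternative).

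**Step 1: reproduce the plan's 80%.** The proportion alive at the cut is the average of exp(-hazard × f) for f from 36 to 60.
- Null: 0.0402, so expected deaths are 30 × 0.9598 = 28.8.
- Alternative: 0.1307, so expected deaths are 30 × 0.8693 = 26.1, and 3.9 patients are alive.

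Power of a one-sample test on the log hazard = Φ[(ln 1.6 − 1.645/√28.8) × √26.1] = Φ(0.835) = 0.798. The stated 80% is reproduced. A one-sample log-rank test with variance (O+E)/2 gives 0.81 in simulation.

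**Step 2: Kaplan-Meier curve in the worst case.** Suppose every patient alive at the cut is censored at month 12 and every later death counts. At a true median of 16 months, S(12) = 0.5946. Of this, 0.1307 is censored at month 12, leaving 0.5946 − 0.1307 = 0.4639 at risk, all of whom die. For t from 12 to 36 months the curve tends to

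0.5946 × [S(t) − 0.1307]/0.4639 = 1.282 × [S(t) − 0.1307].

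| Quantity | True | Worst case |
|---|---|---|
| S(24) | 0.354 | 1.282 × 0.2228 = 0.286 |
| S(36) | 0.210 | 1.282 × 0.0795 = 0.102 |
| Median (months) | 16.0 | 15.1 |

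The median solves S(t) = 0.5/1.282 + 0.1307 = 0.521, so t = 15.1. In simulated trials of 30 patients the typical Kaplan-Meier median moves from 15.3 to 14.9 months.

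**Step 3: why a test on total follow-up loses power.**
- With full follow-up, total time is 26.08/0.04332 = 602 patient-months. Deaths expected under the null hazard are 602 × 0.0693 = 41.7, against 26.1 observed. Typical z = (26.1 − 41.7)/√[(26.1 + 41.7)/2] = −2.7.
- In the worst case, the 3.9 survivors have on average 46 months of follow-up and lose all but 12, about 133 patient-months in total. Total time is 469, expected deaths are 32.5 and observed deaths are still 26.1. Typical z = (26.1 − 32.5)/√[(26.1 + 32.5)/2] = −1.2, short of −1.645.

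**Step 4: simulated results** (200,000 trials of 30 patients, true median 16 months).

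| Alive dates after month 12 | Log-rank power | S(36) |
|---|---|---|
| All survivors updated at cut-off | 0.81 | 0.21 |
| Annual contact for all | 0.76 | 0.21 |
| None for 25% of survivors, rest at cut-off | 0.72 | 0.19 |
| None for 50%, rest at cut-off | 0.61 | 0.16 |
| None for 75%, rest at cut-off | 0.46 | 0.13 |
| None for any survivor | 0.28 | 0.10 |

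The documents do not say which row would apply. At a true median of 10 months, the rejection rate of this test falls from 0.049 with full updating to 0.003 in the worst case.

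**Step 5: the analysis that Section 11.4 does specify.** If success meant a one-sided 95% Brookmeyer-Crowley lower limit above 10 months, power is about 0.50 both with full updating and in the worst case, because that limit is set mainly by data before month 12.

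**The case against.** The strongest reply is that Section 6.4 is not the whole schedule. Section 4.6 promises at least annual follow-up in remission and continued OS follow-up after relapse. Appendix 2 marks its status report without restricting it by remission status, and the annual wording in Section 4.6 favours a once-a-year reading. Relapse and new-therapy dates recorded under Section 6.4 also show that a patient was alive then. The censoring rule refers to the date last known alive, so any dated chart entry could serve. If annual contact does reach everyone, the power loss is about 5 points and the curve at 24 and 36 months is sound. All of this stands, and it makes the 28% figure a worst case. It does not remove the problem. Section 4.6 gives no interval for patients alive after relapse or persistent disease, Appendix 2 can be read two ways, and relapse or therapy dates exist only for patients with those events. A site that follows Section 6.4 as written is compliant.

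A reader might also infer that the plan schedules a 36-month analysis at which the stated 80% power is lost. The documents do not support that. The 36 months is a minimum follow-up in a power assumption, no analysis date is set, and patients are followed for up to 5 years. If the analysis waits for Year-5 status on every patient, the bias does not arise and power is 0.79 to 0.82. Nor does the plan name the log-rank test to which the loss applies, and Section 11 calls the analyses mainly descriptive. For the specified median and interval, the effect is small. The methods that reproduce the stated 80% do, however, use total follow-up time, and these are the ones affected.

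**Conclusion.** The point holds as a contradiction between Sections 4.6, 6.4 and Appendix 2 that leaves the primary endpoint open to outcome-dependent censoring. It takes effect if OS is analysed at the follow-up assumed in Section 11.2, before survivors have Year-5 status, and without a vital-status update.

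The downward bias then falls mainly in the tail. At worst, 36-month OS is about 10% instead of 21%, and one-sample log-rank power is about 28% instead of about 80%. With annual contact for all, power is about 76% with essentially no bias at 24 and 36 months. The Kaplan-Meier median shifts by less than 1 month in every case examined, and a Brookmeyer-Crowley criterion is almost unaffected. The error is conservative: it can hide a benefit but does not raise the risk of a false efficacy claim. The figures rest on exponential survival, uniform 24-month accrual, a true median of 16 months and complete ascertainment of deaths.

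**What to change.** 1. Replace the three descriptions in Sections 4.6, 6.4 and Appendix 2 with one rule: after year 1, record survival status and the last-known-alive date at least annually for every living patient, whatever the remission status or salvage therapy.
2. State the OS data cut-off in Section 11.4.
3. Update vital status for all living patients by phone or chart at that cut-off, and censor each at that contact.
4. Name the test against the 10-month null median, if one is intended, so that the effect of follow-up on power can be judged.

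The cost is protocol wording and a few phone or chart contacts per surviving patient. Under the 16-month assumption about 30 × 0.595 = 18 patients are alive at month 12. No visits or procedures are added. The rule is best set in advance, because a late search may fail for patients who have lost contact with the site.

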## 7 Drug Administration

The responsibility for treatment of patients rests with the individual investigator. Protocol treatment must begin within 72 hours of registration.

**First Induction:**

Agent	Dose	Route	Duration	Schedule
CPX-351	100u/m  /day	IV	90 minutes*	Days 1, 3 and 5

**Second Induction:**

Agent	Dose	Route	Duration	Schedule
CPX-351	100u/m  /day	IV	90 minutes*	Days 1 and 3

**Consolidations (up to 2 are permitted):**

\*Approximately

Agent	Dose	Route	Duration	Schedule
CPX-351	65u/m  /day	IV	90 minutes*	Days 1 and 3

## 7.1 Drug Preparation and Administration

### 7.1.1 CPX-351

#### 7.1.1.1 Drug Preparation

The appropriate number of vials of CPX-351 (cytarabine:daunorubicin) Liposome Injection should be removed from the refrigerator prior to reconstitution. Reconstitute with 19 mL of sterile water for injection using a 20 mL syringe. Do not heat CPX-351 (cytarabine:daunorubicin) Liposome Injection. After reconstitution, invert vials gently 3-4 times and let rest for 15 minutes and repeat vial inversion prior to withdrawing drug for dilution. The concentration of the reconstituted dispersion is 5 u/mL. CPX-351 (cytarabine:daunorubicin) Liposome Injection should be diluted in approximately 500 mL of sodium chloride injection or dextrose injection.

The IV bags and infusion sets must be non-DEHP. Aseptic technique must be strictly observed throughout the handling of CPX-351 (cytarabine:daunorubicin) Liposome Injection since no bacteriostatic agent or preservative is present. The infusion of CPX-351 (cytarabine:daunorubicin) Liposome Injection must be started within 4 hours of dilution. Vials are for single use. Unused material should be recorded as such and discarded according to institutional policies. Procedures for proper handling and disposal of anticancer drugs should be implemented.

#### 7.1.1.2 Drug Administration

The infusion of CPX-351 (cytarabine:daunorubicin) Liposome Injection will be performed through a central venous catheter, using an infusion pump to ensure that the drug is infused over the specified time period. Non-DEHP containing administration sets should be used. **Do not use an in-line filter.** CPX-351 should never be given by the intramuscular or subcutaneous route. Administer CPX-351 over approximately 90 minutes via an infusion pump. Flush the line to ensure administration of the full dose.

The dosage (total units and u/m^2), start/stop time of the infusion, total volume infused, must be documented in the patient's chart.

(Reconstitution information to be obtained from pharmacy as well as infusional instruction)

## 7.2 Drug Accountability

The study pharmacist or designee must maintain records of the delivery of CPX-351 to the study site, the inventory at the site, the use by each patient, and the disposition of unused product. These records should include dates, quantities, lot numbers, expiration dates and patient identifications. Institutions should maintain records that document adequately that the patients were provided the doses specified by the protocol and reconcile all investigational product received from Jazz Pharmaceuticals. Records of storage conditions (temperature logs) must be kept for the entire period that CPX-351 is maintained at the institution.

## 7.3 Dose Reductions and Delays

It is the intention of the study to treat every patient at full dose. Dose delays or modifications will be recommended at the discretion of the treating physician and PI. Doses may be delayed due to toxicities (for example hypersensitivity reactions). Any doses missed or delayed due to toxicity may be administered as soon as the patient has recovered from the toxicity. Toxicities will be graded using the CTCAE Version 4.0. See APPENDIX 4: Common Terminology Criteria for Adverse Events V4.0 (CTCAE)). Toxicities for cytarabine and daunorubicin are relatively well known, and are outlined in the product information for each of these drugs. Furthermore, dose reductions or protocol closure will be considered:

- 1) If >2 of the first 5 patients or >3 of the first 15 patients experience grade 4 toxicities, accrual will stop, the protocol reviewed, and dose modifications considered. If the incidence of grade 4 toxicity exceeds 20% of patients at any point after the first 15 patients have been treated, accrual will stop, the protocol will be reviewed, and dose modifications considered.
  
- 2) If 30-day mortality exceeds 20% (>3 of the initial 15 patients), *all further accrual will stop*. Subsequent enrollment after the first 15 subjects should ideally resume after the safety analysis is complete, however recognizing the acute nature of AML, it might not be possible to deny treatment to subjects in screening for ethical reasons sufficiently long to evaluate safety or efficacy. In other words, if the 30-day mortality for the preceding patients is less than 20%, study accrual will continue during the DSMB's safety analysis.

In the event that more than 15 subjects have enrolled before the safety analysis, only the first 15 subjects dosed will be informative for determining need for dose reduction as outlined in section 4.2.

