### 2.4 Rationale for CPX-351 use in Patients suitable for non-intensive therapy

Three clinical studies have been completed with CPX-351 and a detailed presentation is available in the Investigator's Brochure. A brief summary of observations pertinent to treatment of AML patients, particularly those with co-morbidities and patients whose age tends of limit treatment to non-intensive regimens is discussed below.

The rationale for using CPX-351 to treat older patients thought to be unsuitable for treatment with intensive chemotherapy is rooted in the characteristics of AML in older patients, the pharmacology and mechanism of CPX-351 action, and clinical observations

of the dose-response and safety of CPX-351. It is well known that both the incidence of AML and the risk of AML resistance to chemotherapy increase in an age related manner. Younger patients, particularly those younger than 45 years of age, have higher response rates, lower rates of primary refractory disease, and longer survival than patients over the age of 70. This is associated with an age related rising risk of adverse cytogenetics and multidrug resistance phenotype. CPX-351 packages cytarabine and daunorubicin within liposomes at a 5:1 molar ratio, found *in vitro* to maximize drug synergy and minimize antagonism. CPX-351 liposomes are stable and persist in the plasma for extended periods of time leading to cytarabine and daunorubicin half-lives of approximately 24 hours. This result suggests that CPX-351 may be effective for both in rapidly and slowly cycling leukemias. Exposure of leukemia cells from cell lines and circulating blast cells from patients demonstrate direct entry of CPX-351 liposomes and subsequent intracytoplasmic release of drug. These observations suggest that effective treatment may be possible even in patients with multidrug resistance phenotype due to increased P-glycoprotein expression. Clinical observations of CPX-351 safety and efficacy come almost exclusively from patients considered fit for intensive chemotherapy and indicate a safety profile that is very similar to that of 7+3 chemotherapy except for more prolonged myelosuppression. In the clinic the dose-toxicity/response curve appears to be shallow with most of the grade 3/4 adverse events associated with prolonged myelosuppression rather than severe non-hematologic toxic events.

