Taken together these findings suggest that treatment at the MTD (100 units/m^2/dose on day 1, 3, and 5) is likely to be feasible, even in patients of advanced age and with some comorbidities because the toxicities of treatment are mostly confined to myelosuppression and because supportive care with anti-infective prophylaxis is effective. It is thought that full dose treatment is likely to maximize the probability of response and that response is possible even in patient populations enriched for adverse cytogenetics and multi-drug resistance phenotype. The mode of action of CPX-351 should enable rapid clearance of leukemia from the peripheral blood and bone marrow with most patients achieving complete response after one induction course of treatment with recovery from neutropenia usually within 5-7 weeks.

Treating an AML patient population usually considered suitable for non-intensive regimens with CPX-351 is not without risk. This patient population is expected to be older with some baseline comorbidities and cannot be expected to be as resilient as the fit older population treated in Phase II with CPX-351. In that study induction mortality was assessed at Day 30 and 60 and a lower rate of early mortality was observed for CPX-351 treated patients (4/85, 4.7% vs. 6/41, 14.6% at 60 days, *p*=0.053). This result is the best evidence that CPX-351 treatment at full dose is likely to be acceptably safe and suggests that rapid clearance of leukemia due to full dose treatment may assist in reducing the contribution of leukemia to the early death rate.

The greater myelosuppression and more prolonged neutropenia following CPX-351 treatment was associated with a higher frequency of febrile neutropenia (63.5% vs. 51.2%), grade 3 and 4 infections (e.g. bacteremia (42.4% vs. 22%)), and bleeding events (e.g. epistaxis (36.5% vs. 19.5%)). In spite of this the lower mortality rate at 30 and 60 days

indicates that CPX-351 was safe and strongly suggests that anti-infection prophylaxis was effective in preventing infection-related deaths in spite of risks of myelosuppression.

Most recently, a phase 3 trial comparing CPX-351 to standard induction chemotherapy with daunorubicin and cytarabine in older patients aged 60-75 with high risk AML was completed. The Phase 3 trial compared to the standard of care regimen of cytarabine and daunorubicin known as 7+3.

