### 5 Selection and Withdrawal of Patients

#### 5.1 Study Population

##### 5.1.1 *Inclusion criteria*

- 5.1.1.1 Ability to understand and voluntarily give informed consent
- 5.1.1.2 Age  $\geq 60$  years at the time of study treatment
- 5.1.1.3 Pathological diagnosis of AML according to WHO criteria (with  $> 20\%$  blasts in the peripheral blood or bone marrow) including:
- 5.1.1.4 De novo AML with normal karyotype or adverse karyotypes (including patients with karyotypic abnormalities characteristic of MDS)
- 5.1.1.5 Secondary AML: transformed from prior MDS or MPN, confirmed by bone marrow documentation of prior antecedent hematologic disorder

- 5.1.1.6 Therapy-related AML: t-AML, requires documented history of prior cytotoxic therapy or ionizing radiotherapy for an unrelated disease
- 5.1.1.7 Performance status >50% KPS, ECOG 0-2
- 5.1.1.8 Laboratory values fulfilling the following:
  - 5.1.1.9 Serum creatinine < 2.5 mg/dL
  - 5.1.1.10 Serum total bilirubin < 2.5 mg/dL,
  - 5.1.1.11 Serum alanine aminotransferase or aspartate aminotransferase < 3 times the ULN
  - 5.1.1.12 Patients with elevated liver enzymes and serum creatinine values secondary to AML are eligible after discussion with PI
  - 5.1.1.13 Cardiac ejection fraction  $\geq$  50% by echocardiography, MUGA, or Cardiac MRI
  - 5.1.1.14 Patients with history of second malignancies in remission may be eligible if there is clinical evidence of disease stability off cytotoxic chemotherapy, documented by imaging, tumor marker studies, etc., at screening. Patients maintained on long-term non-chemotherapy treatment, e.g., hormonal therapy, are eligible.

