## **11 Statistical Considerations**

The primary objective of this non-randomized open label study is to evaluate the safety and efficacy of CPX-351 as a treatment for AML in elderly ( $\geq 60$  years of age) patients. Dose reductions or protocol closure will be considered:

- 1) If  $>2$  of the first 5 patients or  $>3$  of the first 15 patients experience grade 4 toxicities, accrual will stop, the protocol reviewed, and dose modifications considered. If the incidence of grade 4 toxicity exceeds 20% of patients at any point after the first 15 patients have been treated, accrual will stop, the protocol will be reviewed, and dose modifications considered.
- 2) If 30-day mortality exceeds 20% ( $>3$  of the initial 15 patients), *all further accrual will stop*. Subsequent enrollment after the first 15 subjects should ideally resume after the safety analysis is complete, however recognizing the acute nature of AML,

it might not be possible to deny treatment to subjects in screening for ethical reasons sufficiently long to evaluate safety or efficacy. In other words, if the 30-day mortality for the preceding patients is less than 20%, study accrual will continue during the DSMB's safety analysis.

In the event that more than 15 subjects have enrolled before the safety analysis, only the first 15 subjects dosed will be informative for determining need for dose reduction as outlined above.

Patients who die within the first 7 days because of leukemia related toxicity will be replaced. Those patients will be included in the analysis given the intention to treat for 30 day mortality and overall survival.

Analyses will primarily be descriptive in nature. Categorical variables will be summarized as frequency counts with associated percentages and continuous variables will be summarized as mean, standard deviation, median and range. Exact confidence intervals will be computed using the Clopper-Pearson method.

All analyses will be performed using SAS version 9.2 or higher.

Additional details regarding statistical analyses may be presented in a Statistical Analysis Plan (SAP).

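### The grade 4 accrual-stopping rule does not exclude hematologic toxicity, so read literally it can halt accrual for the myelosuppression the protocol expects

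*Combined protocol and SAP*

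**What the plan says.** Section 7.3 sets two early limits: "If >2 of the first 5 patients or >3 of the first 15 patients experience grade 4 toxicities, accrual will stop". From then on there is a running limit: "If the incidence of grade 4 toxicity exceeds 20% of patients at any point after the first 15 patients have been treated". Section 11 repeats both and gives the consequence as "accrual will stop, the protocol will be reviewed, and dose modifications considered". The lead-in, which covers this rule and the 30-day mortality rule together, says dose reduction or protocol closure will be considered. Grading is by CTCAE version 4.0. The rule itself names no type of toxicity, no link to study drug and no duration.

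Four other places bear on what would be counted:

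- Section 2.4 reports "most of the grade 3/4 adverse events associated with prolonged myelosuppression rather than severe non-hematologic toxic events" and argues that full dose is feasible because "the toxicities of treatment are mostly confined to myelosuppression". It expects recovery from neutropenia usually within 5 to 7 weeks.
- Section 7.4, on infection prophylaxis, anticipates profound neutropenia and advises cover until the ANC is back to 500/µL.
- Section 9.2.1 includes abnormal laboratory findings in the definition of an adverse event.
- Section 5.2 discontinues a patient for unresolved toxicity of grade 3 or higher, but only if it is treatment-related and non-hematological.

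**The concern.** A toxicity stopping rule is useful when crossing it signals something the investigators did not already expect. Here the counted event is left open, and the protocol's own description of the drug puts its main expected effect inside the open category. Section 5.2 shows that the drafters wrote a hematologic exclusion where they wanted one; the accrual rule has none.

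Two things are at stake. First, a 30-patient study could pause, and its dose come under review, because of cytopenias that the rationale treats as the price of full-dose therapy, although 7.3 says the intention is to treat every patient at full dose. Second, a crossing would carry little information: the count would be the same whether it came from expected neutropenia or from unexpected organ toxicity. If the investigators instead set cytopenias aside informally, the trigger would rest on a judgment the protocol does not record.

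**Working it through.** The plan gives no operating characteristics for this rule and no assumed grade 4 rate, so there is no figure to reproduce.

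**Inputs from the documents (7.3 and 11).** Stop if 3 or more of the first 5, or 4 or more of the first 15, have a grade 4 toxicity; after patient 15, stop if the proportion exceeds 20%. The limits agree with each other, since 3/15 = 20% and a fourth event exceeds it.

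**Assumption.** Each patient independently has probability p of a counted event. Because p is not in the documents, a range is shown.

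**Formula for a stop by patient 15.** With X5 the count in the first 5 patients and Y the count in the next 10:

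P(stop by 15) = 1 − Σ over x = 0, 1, 2 of P(X5 = x) × P(Y ≤ 3 − x)

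**Worked at p = 0.2.**

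- x = 0: 0.3277 × 0.8791 = 0.2881
- x = 1: 0.4096 × 0.6778 = 0.2776
- x = 2: 0.2048 × 0.3758 = 0.0770
- No stop: 0.6427. Stop: 1 − 0.6427 = 0.3573, or 36%.

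**Worked at p = 0.4.**

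- x = 0: 0.0778 × 0.3823 = 0.0297
- x = 1: 0.2592 × 0.1673 = 0.0434
- x = 2: 0.3456 × 0.0464 = 0.0160
- No stop: 0.0891. Stop: 1 − 0.0891 = 0.9109, or 91%.

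**Formula for a stop by patient 30.** The same calculation is carried forward one patient at a time, ending whenever the count at patients 16 to 30 exceeds 0.20 × n.

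| p | Limit at 5 alone | Limit at 15 alone | Either, by patient 15 | Any limit, by patient 30 |
|---|---|---|---|---|
| 0.1 | 1% | 6% | 6% | 14% |
| 0.2 | 6% | 35% | 36% | 65% |
| 0.3 | 16% | 70% | 71% | 94% |
| 0.4 | 32% | 91% | 91% | over 99% |
| 0.5 | 50% | 98% | 98% | over 99% |

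The last two entries on the right follow because the probability rises with p and is already 99.4% at p = 0.39. The chance of a stop by patient 15 reaches 90% at p = 0.392. Nearly all of it comes from the limit at 15.

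**What p refers to.** If cytopenias count, p is the chance that a patient has any grade 4 toxicity, hematologic or not. If they do not, p is the chance of a grade 4 non-hematologic toxicity, which 2.4 suggests is the smaller part. The protocol therefore does not settle which row of the table applies.

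**The case against.** The best case against is that the drafters plainly meant non-hematologic events. In 7.3 the example of a toxicity that delays a dose is a hypersensitivity reaction. Exclusion criterion 5.1.2.4 requires toxicities of prior therapy to have recovered to grade 1 or less, with only 7 days required since a hypomethylating agent; if that word covered cytopenias, many of the pretreated patients the study invites would seem to be barred. It would also be odd for a protocol that defends full dose because toxicity is mostly myelosuppression to cut the dose for myelosuppression.

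This stands as evidence of intent, and it makes the scope ambiguous. It does not exclude cytopenias. Limiting the rule to drug effects does not help either: 7.3 says "Toxicities for cytarabine and daunorubicin are relatively well known", and 2.4 names myelosuppression as the main one.

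A second objection is that a cautious trigger suits patients whom 2.4 expects to be less resilient than the earlier fit population. That is a fair defense of the numerical limits, but not of leaving the counted event undefined.

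Some stronger readings are tempting and are not supported:

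- *A stop is nearly certain.* This needs a grade 4 rate, and there is none. In 2.4, febrile neutropenia (63.5%) has no grade attached, and bacteremia (42.4%) is offered as an example of grade 3 and 4 infection with no split.
- *Crossing the limit ends the trial.* The rule requires a stop, a review and consideration of dose changes. Closure appears only in the lead-in, as something to be considered.
- *A stopped trial has no way forward.* Section 11.7 lets the DSMB convene when stopping criteria are met and sends its recommendations to the IRB.
- *Cytopenias present at entry would count.* Section 9.2.1 records events from the start of the Day 1 infusion and includes worsening of existing conditions, which largely answers this.

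**Conclusion.** The concern holds as a fault in how the rule is written. The rule counts grade 4 toxicity without excluding hematologic events, in a protocol that expects toxicity to be mainly hematologic. Followed as written, it can pause accrual and prompt a dose review for an expected effect.

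The size depends on an unknown rate. At p between 0.2 and 0.5, the chance of a stop by patient 15 runs from 36% to 98%. These figures assume independent patients and a common p. The expected myelosuppression makes the upper part of the range plausible if cytopenias are counted, but the documents do not establish it, nor do they establish that the investigators would count them.

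The harm is limited to an avoidable pause and a safety signal of low specificity. Overall survival, 30-day mortality and the other endpoint estimates are not biased, and the mortality stopping rule is unaffected.

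**What to change.** In both 7.3 and 11, define the counted event as treatment-related non-hematologic grade 4 toxicity, plus grade 4 cytopenia lasting 56 days or more without persistent leukemia. The 56 days comes from the prolonged-cytopenia category in the synopsis safety variables, which carries no grade, and matches the recovery window in 4.5; the clinicians should confirm it. Leave the numerical limits and the 30-day mortality rule unchanged. The table above then gives the rule's behavior with p as the rate of the narrower event: 6% by patient 15 and 14% by patient 30 at a 10% rate, 36% and 65% at a 20% rate.

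The change is one definition, inserted twice. Its cost is less sensitivity to short cytopenias, though these remain visible in the adverse event and laboratory tables of 11.6 and in the DSMB reviews of 11.7. The prolonged-cytopenia component is known only after 56 days, so that part of each look will lag.
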